#### 2.8.5.2 Vital signs

Vital sign assessments are performed in order to characterize basic body function. The following parameters were collected: height (cm), weight (kg), body temperature (°C), heart rate (beats per minute), systolic and diastolic blood pressure (mmHg).

#### Data handling

Vital signs collected on treatment will be summarized. Values measured outside of on treatment period will be flagged in the listings.

#### Data analysis

For analysis of vital signs the clinically notable vital sign criteria are provided in Table 2-5 below.

Vital sign (unit)	Clinically notable criteria	
	above normal value	below normal value
Weight (kg)	increase >= 10% from Baseline	decrease >= 10% from Baseline
Systolic blood pressure (mmHg)	>=180 with increase from baseline of >=20	<=90 with decrease from baseline of >=20
Diastolic blood pressure (mmHg)	>=105 with increase from baseline of >=15	<=50 with decrease from baseline of >=15
Pulse rate (bpm)	>=100 with increase from baseline of >25%	<=50 with decrease from baseline of > 25%
Body temperature (°C)	>= 39.1	-

 Table 2-5
 Clinically notable changes in vital signs

The number and percentage of patients with notable vital sign values (high/low) will be presented.

A listing of all vital sign assessments will be produced and notable values will be flagged. In the listing, the assessments collected outside of on-treatment period will be flagged.

## 2.8.6 Safety during Extension Phase

Safety analyses for the Extension Phase will be performed on the Safety Set in Extension Phase. The assessment of safety will be based mainly on the frequency of AEs and SAEs. The following summaries will be provided:

- Adverse events (refer to Section 2.8.1)
- Adverse events of special interest (refer to Section 2.8.2)
- Deaths (refer to Section 2.8.3)

## 2.9 Pharmacokinetic endpoints

Not applicable.

## 2.10 PD and PK/PD analyses

Not applicable.

## 2.11 Patient-reported outcomes

The PRO Analysis Set will be used for analyzing PRO data unless specified differently. The FACT-B quality of life questionnaire (see Appendix 2 of the protocol) will be used to explore patient-reported outcome measures of health-related quality-of-life, functioning, disease symptoms and treatment-related side effects in selected countries including United States, Canada, United Kingdom, France, Italy and Spain. Due to the nature of the questionnaire and validation, only females will be asked to complete this questionnaire. Scores will be added to create subscale and overall scores. A Trial Outcome Index is generated via addition of the physical well-being, functional well-being, and breast cancer subscales.

The PRO instruments are planned to be administered during screening, every cycle during the first 6 cycles, cycle 8, cycle 10, cycle 12, and every 3 cycles thereafter until the end of treatment (See Table 2.6). Collection of the FACT-B PRO have a  $\pm$ 3 days window unless otherwise indicated.

The baseline is defined as the last PRO assessment on or prior to start of treatment.

No formal statistical tests will be performed for PRO data and hence no multiplicity adjustment will be applied. Descriptive statistics will be used to summarize the subscale and overall scores at each scheduled assessment time point.

Subscale scores from the FACT-B will be displayed as mean profiles, presented over time using time windows as described in Section 2.1. Change from baseline in the subscale scores at the time of each assessment will also be summarized. Patients with an evaluable baseline

Novartis	Confidential	Page 36
SAP	22-Feb-2022 (1:27)	CLEE011A2404

score and at least one evaluable post baseline score during the treatment period will be included in the change from baseline analyses.

Cycle	Day	Time
Cycle 1 Day 1	1	Prior to drug dosing.
Cycles 2 to 6	Every cycle during the first 6 cycles	
Cycles 7 and subsequent	Every 2 cycles: Cycle 8,10, 12. Every 3 cycles: Cycle 15, 18, 36)	
End of treatment	Day of the end of treatment assessment	

 Table 2-6
 Patient reported outcomes collection plan

Compliance to the schedule of administration of PRO will be summarized, for baseline and post-baseline on treatment assessments. The following categories, as collected on the eCRF, will be used to describe whether the questionnaire was completed at a specific time point:

- 1. yes, fully completed
- 2. yes, partly completed
- 3. no, device not available
- 4. no, patient missed scheduled assessment visit
- 5. no, patient refused due to poor health
- 6. no, patient refused (unrelated to health)
- 7. no, study staff felt patient was too ill
- 8. no, questionnaire not available in appropriate language
- 9. no, technical issue
- 10. no, institutional error
- 11. no, other.

If more than 50% of the items are missing in a scale or subscale, the score for this scale or subscale will be considered missing for this assessment. Otherwise, the average of the non-missing items in the scale or subscale will be used to impute for the missing items when calculate the score for the scale or subscale.

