10.1.7 Other analysis sets

The patient-reported outcomes (PRO) will be collected in subgroup of patients in selected countries. The PRO Analysis Set (PAS) consists of all patients in the FAS population for whom baseline and at least one post baseline PRO measurements are available.

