10.5.4 Patient-reported outcomes

FACT-B questionnaire will be used to collect patient reported outcome data in this trial. Scores will be added to create subscale and overall scores. A Trial Outcome Index is generated via the addition of the physical well-being, functional well-being, and breast cancer subscales.

No formal statistical tests will be performed for patient-reported outcomes (PRO) data and hence no multiplicity adjustment will be applied. The PRO analysis set will be used for analyzing PRO data.

Descriptive statistics will be used to summarize the subscale and overall scores at each scheduled assessment time point. Additionally, change from baseline at the time of each assessment will be summarized. PRO data may be summarized by country/region.

Patients with an evaluable baseline score and at least one evaluable post baseline score during the treatment period will be included in the change from baseline analyses.

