## 2.2.5 Other

The patient-reported outcomes (PRO) will be collected in subgroup of patients in selected countries. The PRO Analysis Set consists of all female patients in the FAS population for whom baseline and at least one post baseline PRO measurements are available.

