## Patient Classification:

Patients may be excluded from the analysis populations defined above based on the protocol deviations entered in the database and/or on specific patient classification rules defined in Table 2-2.

ontonia		
Analysis set	Protocol deviations leading to exclusion	Non protocol deviation leading to exclusion
FAS	No written informed consent	No dose of study medication for Core Phase
Safety set in Core Phase	No written informed consent	No dose of study medication for Core Phase
PRO Analysis Set	No written informed consent	No dose of study medication or no post baseline PRO measurements for Core Phase
Safety set in Extension Phase	No written informed consent	No dose of study medication for Extension Phase

Table 2-2	Patient classification based on protocol deviations and non-PD
	criteria

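### By the SAP's default rule, FACT-B compliance is computed only in women selected for having returned forms, so baseline compliance is about 100% by construction and later compliance may be overstated.

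*SAP*

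**What the plan says.** SAP 2.11 sets a default: "The PRO Analysis Set will be used for analyzing PRO data unless specified differently". Protocol 10.5.4 sets the same default with no exception: "The PRO analysis set will be used for analyzing PRO data".

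Under SAP 2.2.5 the set "consists of all female patients in the FAS population for whom baseline and at least one post baseline PRO measurements are available". Protocol 10.1.7 imposes the same two measurement conditions without the word female. That makes no practical difference, because only women are asked to complete the form. The PRO baseline is defined in SAP 2.11: "The baseline is defined as the last PRO assessment on or prior to start of treatment".

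The compliance paragraph, also in SAP 2.11, reads: "Compliance to the schedule of administration of PRO will be summarized, for baseline and post-baseline on treatment assessments". It lists eleven completion categories: two for forms fully or partly completed, and nine reasons for non-completion such as refusal, illness, language or a technical problem. It names no analysis set and no denominator.

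Table 2-2 in the SAP gives this non-deviation ground for exclusion from the PRO Analysis Set: "No dose of study medication or no post baseline PRO measurements for Core Phase". A missing baseline measurement is not listed there.

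**The concern.** A compliance table tells the reader how many of the women who should have returned a form did so, and why the others did not. The PRO Analysis Set is reasonable for scores and change from baseline. As a denominator for compliance it is circular, because a woman enters it only by having returned forms.

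FACT-B is a named secondary endpoint, summarised descriptively in a single-arm, open-label study. The compliance table is the main evidence on whether the mean score profiles describe all the women asked, or mainly those well enough to keep answering. A baseline row fixed near 100% gives no such evidence, and the later rows could look better than they are.

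**Working it through.** The documents state no compliance rate and no number of women asked to complete FACT-B, so there is no planned figure to reproduce. The check is on the denominator. All rates below are assumptions.

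**Which denominator applies.** SAP 2.11 gives the default set, and nothing in the compliance paragraph overrides it. SAP 2.1.2 takes percentages over the relevant population or subgroup. Together these make the PRO Analysis Set the denominator.

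**Notation.**
- b: share of eligible women with a baseline measurement.
- z0: share of women still due forms who return no post-baseline form, taken as independent of having a baseline.
- q: completion at a given later visit among women who return at least one later form.

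**Baseline.** Compliance in all eligible women is b. In the PRO Analysis Set every member has a baseline measurement, so it is about 100%. For b = 80% to 95%, the table would show about 100% throughout.

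**Later visits.** Compliance in all women still due the form is (1 - z0) × q. In the PRO Analysis Set it is q. The ratio is 1/(1 - z0). With q = 85%:

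| z0 | All women due a form | PRO Analysis Set | Ratio |
|---|---|---|---|
| 5% | 0.95 × 85% = 80.75% | 85% | 1.05 |
| 10% | 0.90 × 85% = 76.5% | 85% | 1.11 |
| 20% | 0.80 × 85% = 68.0% | 85% | 1.25 |

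**When the later effect is small.** Suppose all women share one completion rate p, independent across m forms due. Conditioning on at least one form gives p/(1 - (1 - p)^m). For p = 0.80:
- m = 1: 0.80/0.80 = 1.000
- m = 2: 0.80/0.96 = 0.833
- m = 3: 0.80/0.992 = 0.806
- m = 5: 0.80/0.99968 = 0.800

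The schedule has 16 post-baseline cycle visits up to Cycle 36 (Cycles 2 to 6, 8, 10, 12, then every third cycle from 15 to 36). Material inflation therefore comes from women who never return a later form, and from women with few forms due.

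**Could women excluded only for lacking a baseline offset this?** If their later compliance is r, the overall rate is b(1 - z0)q + (1 - b)r. Setting this equal to q gives r = q[1 - b(1 - z0)]/(1 - b). With b = 0.90, z0 = 10% and q = 85%, r = 0.85 × 0.19/0.10 = 1.615, which is impossible. Over b = 0.80, 0.90 and 0.95 and z0 = 5%, 10% and 20%, the smallest break-even is 1.02 (b = 0.80, z0 = 5%). No offset was possible in any scenario tried.

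**The case against.** **The denominator is inferred.** No sentence says that compliance uses the PRO Analysis Set. Completion status is described as collected on the eCRF, whereas FACT-B answers come through a vendor's ePRO system (protocol 9.3.2 and 9.4). It could therefore be read as form tracking outside the default. Asking for baseline compliance with nine reasons for non-completion also suggests that a wider denominator was intended. Both readings are plausible, but no text supports either. The default yields only when something different is specified, and nothing is.

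**Baseline reasons can still occur.** A reader might infer that no baseline non-completion code can ever appear. That goes too far. SAP 2.11 mentions administration during screening, so a woman with a screening form who missed Cycle 1 Day 1 is in the set and can carry such a code. A partly completed form may also qualify a woman for the set, so the 100% applies to the two completed categories together.

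**Table 2-2.** A reader might take it as a rival definition of the set. It lists exclusions from sets already defined, so it is incomplete rather than contradictory. If it alone were programmed, baseline compliance would not be about 100% by construction, but women with no later form would still be dropped.

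**A large Cycle 2 gap is not established.** Suppose 90% have a baseline, 10% of those return nothing later, and 85% of baseline completers return Cycle 2. The set holds 0.90 × 0.90 = 81% of women, and reported compliance is 0.765/0.81 = 94%. Over all eligible women, the true figure lies between 76.5% and 86.5%, depending on the women without a baseline. That comparison assumes that women who return nothing later stay on treatment. If those 9% had left before Cycle 2 and all women without a baseline remained, the denominator is 0.91 and the range is 0.765/0.91 to 0.865/0.91, or 84% to 95%, which contains 94%.

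**Existing safeguards.** Post-baseline compliance is already limited to on-treatment assessments, and SAP 2.3.8 reports the size of each analysis set. Neither supplies a compliance rate over the women asked. If SAP 2.1.2 were applied literally at every visit, women off treatment would stay in the later denominators and pull reported compliance down. The direction at late visits is thus less certain than at baseline.

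**Conclusion.** The point holds on the plan as written. Under the SAP 2.11 default, baseline FACT-B compliance is about 100% by construction and its non-completion reasons are nearly empty. This needs no assumed rate. It rests only on the default set applying to the compliance table and on the membership rule in SAP 2.2.5 and protocol 10.1.7.

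At later visits, with women still due a form as the reference, the overstatement is a factor of about 1/(1 - z0). The documents give no value for z0, and the effect may be small if few women still on treatment return no later form. They do not support a specific percentage-point gap, nor the conclusion that non-completion is hidden altogether: post-baseline reasons are still tabulated for members of the set.

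The consequence is limited to a quality measure for a descriptive secondary endpoint. No FACT-B score and no primary safety result changes. It is still worth correcting, because the planned baseline summary cannot inform.

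**What to change.** In SAP 2.11, state that compliance is computed in female FAS patients in the countries or sites where FACT-B is collected. At baseline the denominator is all of them. At each later visit it is those still on study treatment with a form due. Keep the PRO Analysis Set for score and change-from-baseline summaries. In Table 2-2, add a missing baseline measurement to the exclusions for the PRO Analysis Set, so that it matches SAP 2.2.5.

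The cost is one sentence, one changed table denominator and one Table 2-2 entry. The SAP describes the completion categories as collected on the eCRF, so no new data should be needed. The downside is that reported compliance may look less favourable.

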## 2.12 Biomarkers

Not applicable.

## 2.13 Other Exploratory analyses

Not applicable.

Novartis	Confidential	Page 37
SAP	22-Feb-2022 (1:27)	CLEE011A2404

## 2.14 Interim analysis

Interim analyses (IA) may be performed periodically, if needed, to fulfill regulatory requests, safety updates or for publication purposes. The IAs are planned to be performed about 12 months after FPFV, and annually thereafter for publication purposes.

Safety analyses (see Section 2.8) will be performed in IA and it will include all patients up to the data cut-off date. PRO analyses (see Section 2.11) and Efficacy analyses (see Section 2.7) will include patients who have progressed or dead, or discontinued, or who have at least 6 cycles of treatments before the cut-off date. Subgroup (see Section 2.2.5) analyses will only be performed if at least 100 patients are present in each subgroup.

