4.1 Description of study design

This is an open-label, single arm, multi-center Phase IIIb study to evaluate the overall safety and tolerability and clinical efficacy of ribociclib in combination with letrozole in men and pre/postmenopausal women with HR+, HER2- aBC and no prior hormonal treatment for advanced disease. Gonadal suppression is achieved with either goserelin or leuprolide in men and premenopausal women patients.

The study will be composed of 2 phases:

- Core Phase: from FPFV to 18 months after LPFV. During the Core Phase, safety and efficacy data (including PROs in selected countries) will be collected;
- Extension Phase: from the end of the Core Phase to LPLV. In the event study patients are still deriving benefit at the end of the Core Phase and ribociclib is not approved or available and reimbursed, patients may be transitioned to this Extension Phase and continue to receive the drugs until progression, intolerance, death or physician/patient decision; only safety and clinical benefit (as assessed by investigator) data will be collected.

Approximately 3,000 patients across a diverse number of sites, countries, and regions are expected to be enrolled in this trial. Study treatment of the Core Phase will be provided until disease progression, death, unacceptable toxicities, physician's decision, subject/guardian's decision, protocol deviation, study termination by sponsor, lost to follow-up, technical problems or until 18 months after LPFV, whichever event occurs first (See Figure 4-1).

Enrollment in this trial is not competitive, with the purpose to include a diverse patient population in terms of sites, countries and regions. Each participating country will be assigned a predefined number of patients (based on number of participating sites and available patient population); once this number is achieved, countries may stop enrollment while the study will continue to enroll in other countries/regions. Safety data collected will include all AEs and SAEs including grade 3/4 AEs, events of special interest (Neutropenia including febrile neutropenia, QT prolongation, hepatobililary toxicity), AEs leading to permanent treatment discontinuation or death, vital signs, physical examination, variation of the ECOG performance status, and selected hematology/chemistry parameters at study visits while the patient remains on study and for 30 days after discontinuation.

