Time to Tumor Progression (TTP) and overall tumor response (ORR/CBR) will be assessed by the investigator using RECIST v1.1 criteria. Tumor assessments should be performed every 12 weeks (recommended timeframe) or according to the current standard of care (as per local requirements) during treatment phase and at end of treatment (EOT). It is strongly recommended that a tumor assessment is performed before the patient is switched to a new antineoplastic therapy.

Local/regional sub-studies/analysis can be conducted in the patient population enrolled in [CLEE011A2404] (CompLEEment-1) study. These sub-studies can be designed to explore additional aspects of ribociclib treatment in HR+HER2- advanced breast cancer, which are not

assessed in the current CLEE011A2404 protocol. Examples of sub-studies include biomarker analysis (correlative science studies), additional patient-reported outcome (PRO) evaluations or any other relevant assessments that are not currently evaluated during CLEE011A2404 study. Sub-study protocols must follow the current Novartis process for review and approval of sponsored clinical trials, and should be reviewed and approved by the relevant regulatory authorities and Ethics Committees before implementation.

Figure 4-1 Study design

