14.3.21 Time to progression

Some studies might consider only death related to underlying cancer as an event which indicates progression. In this case the variable "Time to progression" might be used. TTP is defined as PFS except for death unrelated to underlying cancer.

Time to progression (TTP) is the time from date of randomization/start of treatment to the date of event defined as the first documented progression or death due to underlying cancer. If a patient has not had an event, time to progression is censored at the date of last adequate tumor assessment.

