## 2.1.1 Data included in the analysis

The analysis cut-off date for the final analysis of the Core Phase will be established after all enrolled patients have completed at least 18 months of treatment or have discontinued study. Interim analyses (IA) are planned to be performed periodically. The first IA planned to be performed about 12 months after FPFV, and periodically if needed to fulfill regulatory requests, safety updates, or for publication purposes. All statistical analyses will be performed using all data collected in the database up to the data cut-off date. All data with an assessment date or event start date (e.g. vital sign assessment date or start date of an adverse event) prior to or on the cut-off date will be included in the analysis. Any data collected beyond the cutoff date will not be included in the analysis and will not be used for any derivations.

Novartis	Confidential	Page 14
SAP	22-Feb-2022 (1:27)	CLEE011A2404

Final analysis of the Extension Phase will be performed when all patients have been followed for 30 days after they have either prematurely discontinued or been discontinued from the study after completing treatment as per protocol.

All events with start date before or on the cut-off date and end date after the cut-off date will be reported as 'ongoing'. The same rule will be applied to events starting before or on the cutoff date and not having documented end date. This approach applies, in particular, to adverse event and concomitant medication reports. For these events, the end date will not be imputed and therefore will not appear in the listings.

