## Clinical benefit rate (CBR)

CBR is defined as the proportion of patients with a best overall response (BOR) of confirmed CR or PR, or SD lasting 24 weeks or longer, according to RECIST 1.1 criteria. A patient will be considered to have SD for 24 weeks or longer if a SD response is recorded at 23 weeks or later from enrollment, allowing for the  $\pm 1$  week visit window for tumor assessments. Patients with only non-measurable disease at baseline will be part of the analysis and will be included in the numerator only if they achieve a complete response or have a 'Non-CR/Non-PD'

Novartis	Confidential	Page 30
SAP	22-Feb-2022 (1:27)	CLEE011A2404

response 23 weeks or more after enrollment. CBR will be calculated using the FAS based on the investigators' tumor assessments.

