#### 2.7.3 Handling of missing values/censoring/discontinuations

TTP will be censored at the date of the last adequate tumor assessment if no TTP event is observed prior to the analysis cut-off date or the date when a new anti-neoplastic therapy or another investigational treatment for cancer is started, whichever occurs earlier. The censoring date will be the date of last adequate tumor assessment.

The date of last adequate tumor assessment is the date of the last tumor assessment with overall lesion response of CR, PR or SD before an event or a censoring reason occurred. In this case the last tumor evaluation date at that assessment will be used. If no post-baseline assessments are available (before an event or a censoring reason occurred) then the start date of treatment will be used.

In particular, TTP will be censored at the last adequate tumor assessment if one of the following occurs: absence of event, the event occurred after two or more missing tumor assessments. The term "missing adequate tumor assessment" is defined as a tumor assessment (TA) not performed or tumor assessment with overall lesion response of "UNK". The rule to determine number of missing TAs is based on the time interval between the date of last adequate tumor assessment and the date of an event.

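### SAP 2.14 selects interim efficacy and PRO patients partly on outcome, so an early interim TTP curve can only equal or fall below the all-treated curve (minor)

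*SAP*

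**What the plan says.** SAP 2.14 places the interims "about 12 months after FPFV, and annually thereafter for publication purposes". Interim safety analyses take in every patient up to the cut-off. Interim PRO analyses (SAP 2.11) and efficacy analyses (SAP 2.7, that is TTP, ORR and CBR) are narrower: they "will include patients who have progressed or dead, or discontinued, or who have at least 6 cycles of treatments before the cut-off date".

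The rest of the plan points the other way. SAP 2.7 assesses efficacy in the FAS, and SAP 2.1.1 says that analyses use all data up to the cut-off. Short follow-up in TTP is already handled in SAP 2.7.3: "TTP will be censored at the date of the last adequate tumor assessment" when there has been no event. The protocol has the same rule in Appendix 14.3.21: "If a patient has not had an event, time to progression is censored at the date of last adequate tumor assessment". Protocol 10.7 leaves interim details to the SAP, and neither document gives a reason for the restriction.

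**The concern.** Take two patients who started on the same day and have fewer than six cycles at the cut-off. The one who has progressed is analysed; the one who is event-free on treatment is not. That is selection on the outcome being estimated.

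For TTP the direction is certain. An event is progression or death from the cancer, and both are routes into the set, so no dropped patient can have an event. All the events stay while the risk sets shrink.

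The first planned interim falls during accrual, when many patients have short follow-up, and its stated purpose is publication. SAP 2.7.2 asks for Kaplan-Meier estimates at 3 and 6 months among others, which is where the effect would appear. ORR, CBR and PRO use the same selected set.

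**Working it through.** The plan gives no figure for the interim set or its effect, so there is none to reproduce.

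**Direction.** Each Kaplan-Meier factor is 1 − d/n. Dropping only censored patients leaves every d unchanged and makes every n equal or smaller, so each factor falls or stays the same. In 5,000 random data sets the restricted curve was never above the full one.

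**Inputs for the size**
- FPFV 30-Nov-2016, day 0 (Protocol, Amendment 01 rationale). Interim cut-off day 365.
- 1,008 enrolled by 8-Aug-2017, day 251 (Amendment 02). Last first visit 22-Mar-2018, day 477, with 3,255 enrolled (Amendment 03).
- Scans every 84 days: "Tumor assessments should be performed every 12 weeks (recommended timeframe) or according to the current standard of care" (Protocol 4.1).
- Six 28-day cycles: 168 days if completed, 140 days if the sixth has only been reached.
- Assumption: exponential TTP with median 25.3 months. This is the PFS median of the ribociclib arm in the earlier phase III trial (Protocol 1.1.1), borrowed for TTP.

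**Closed form, no dropout.** Event probability per scan interval: p = 1 − 0.5^(84/30.4375/25.3) = 0.0728. In all treated patients the 6-month rate is (1 − p)² = 0.9272² = 86.0%.

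Let A be the patients with at least 168 days of follow-up and B those with 84 to 167 days. The SAP rule keeps all of A, but from B only those who progressed at week 12. The week-12 hazard becomes q = p(A + B)/(A + pB). The week-24 factor is unchanged, because only A has a week-24 scan. The 6-month rate is (1 − q)(1 − p).

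- Uniform accrual, A:B = 197:84. q = 0.0728 × 281/(197 + 6.1) = 0.1007. Rate 0.8993 × 0.9272 = 83.4%, **2.6 points low**.
- Linear accrual through the documents' counts. A = 1,008 × 197/251 = 791; B = 1,008 × 54/251 + 2,247 × 30/226 = 515. q = 0.0728 × 1,306/(791 + 37.5) = 0.1148. Rate 0.8852 × 0.9272 = 82.1%, **3.9 points low**.
- 140-day reading, uniform (225:56): q = 0.0893, rate 84.4%, **1.5 points low**. Documents' counts (904:403): q = 0.1020, rate 83.3%, **2.7 points low**.

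**Simulation with 10% yearly discontinuation, 168 days.** SAP rule against all treated: 83.0% v 85.6% (uniform) and 81.9% v 85.8% (documents' counts), matching the closed form.

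**Sensitivity (points low, 168 days unless stated)**

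| Change | Shortfall |
|---|---|
| Scan dates spread ±7 days | 1.6 to 2.5 |
| Median 30 months / 20 months | 2.2 to 3.5 / 3.0 to 4.7 |
| Scans every 4 weeks | 4.1 to 6.5 |
| Accrual rising up to day 251 | 6.0 to 6.4 |
| 85% enrolled by 12 months | 7.6 to 7.7 |
| Smallest scan-based case (140 days, median 30 months, spread scans) | 0.8 |

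Progression detected with no scan delay is a limiting case and gives more: 3.0 to 7.7 under the main accrual patterns, and 11.3 to 14.2 with steep late accrual at 168 days.

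**When the effect ends.** Day 477 + 168 = 645, which is 645/30.4375 = 21.2 months after FPFV. If the first dose came 28 days after the first visit, it is 673/30.4375 = 22.1 months. At a 24-month cut-off the modelled difference is 0.

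**Deleting only the outcome clause.** With at least six cycles alone, anyone who progressed and stopped at week 12 is removed. The week-12 factor becomes 1 and the 6-month rate is 1 − p = 92.7%, against 86.0%: 6.7 points too high. Simulation gives 92.7% v 85.9%.

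**The case against.** The strongest reply is that little depends on this. Only an interim before about 22 months is touched. The 12-month point, about 30-Nov-2017, had passed before the last SAP amendment of 18-Dec-2019. The SAP says only that interims may be performed. TTP is a secondary, descriptive endpoint in a single-arm safety study with no hypothesis test (SAP 2.5.2) and no data monitoring committee (Protocol 8.6). All of that stands, and it sets the severity.

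It is also fair that the size depends on the comparator. Under the assumed exponential the true 6-month rate is 0.5^(6/25.3) = 84.8%. Scan delay puts the all-treated curve above that. Against 84.8% the SAP-rule values of 83.0% and 81.9% are 1.8 and 2.9 points low.

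The wish for a minimum follow-up is reasonable for ORR and CBR, since a recent starter has had no chance to reach week 24. That supports a limit on start date. It does not support admitting short-follow-up patients only when they have failed.

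A reader might infer three stronger things:
- *The reported or final TTP is biased.* The final Core cut-off comes "after all enrolled patients have completed at least 18 months of treatment or have discontinued study", so the rule has nothing to exclude there. In the Extension Phase "only safety and clinical benefit (as assessed by investigator) data will be collected", so there is no TTP to distort. The documents do not show that an early efficacy interim was produced.
- *ORR, CBR and PRO are biased downward in the same way.* The risk-set argument is specific to Kaplan-Meier. No size has been established for these endpoints, and for PRO no direction either.
- *The shortfall is a known 2.5 to 4 points.* That follows only from 168 days, exact 12-week scans and two accrual shapes. The 12-week interval is only a recommendation.

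**Conclusion.** The rule is wrong as written, and the point is minor. The direction for interim TTP is exact, relative to all treated FAS patients at the same cut-off: equal or lower, never higher. The size is illustrative. At a 12-month cut-off, with an exponential median of 25.3 months and 12-week scans, the 6-month rate is about 1.5 to 4 points low for six cycles read as 140 to 168 days, under uniform or piecewise-linear accrual. Other accrual or scan patterns that were run give about 1 to 8 points. This is not a bound.

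Interim safety keeps all patients. Interims at about 24 months or later and the final Core analysis are essentially unaffected, and no test or decision depends on the interim. The SAP document history lists no change to 2.14, so the rule appears to have been in force at the 12-month point.

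**What to change.** Replace the whole inclusion sentence in SAP 2.14, including the six-cycle criterion. Do not simply strike the outcome clause, for the reason shown in the last step of the working. The new text should say:

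- **TTP:** all FAS patients treated by the cut-off, with the censoring in SAP 2.7.3.
- **ORR and CBR:** all FAS patients (for ORR, those with measurable disease at baseline) first dosed at least 25 weeks before the cut-off, whatever their status. SAP 2.7.1 credits stable disease when "a SD response is recorded at 23 weeks or later from enrollment", allowing one week either side of week 24, so 25 weeks lets that scan fall before the cut-off.
- **PRO:** the PRO Analysis Set summarised by visit, with no selection on progression, death or discontinuation. The 25-week limit rests on the tumor scan and has no basis for FACT-B.

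Label or re-run any early interim efficacy output produced under the present rule.

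The cost is one replaced passage, plus a label or re-run if such an output exists. The downside is that recent starters are left out of interim ORR and CBR. At a 12-month interim the modelled 25-week cohort is about 700 to 1,300 patients, before the measurable-disease restriction for ORR, against about 780 to 1,470 under the present rule.
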